### 2.3.3 ASSESSMENT OF POTENTIAL RISKS AND BENEFITS

Overall, the risks to both mentor and mentee participants are no more than minimal above usual clinical practice and there are substantial potential benefits to intervention participants' clinical outcomes, as well as improvements in the efficiencies of delivery of dialysis care.

Protection of confidentiality. Participant confidentiality will be carefully protected. Facility staff will not be allowed access to trial data (single-blinded design). All research staff will complete the Collaborative Institutional Training Initiative computer-based training program which includes a module on privacy and confidentiality. All study documents will include participants' ID rather than personal names and these include survey documents and assessments. Only one form will link participants' names and study IDs and this will be stored in a password protected and encrypted file overseen by the site PI. Publication of study results will not reveal any identifiable information.

## 3 OBJECTIVES AND ENDPOINTS

Table 3.

OBJECTIVES	ENDPOINTS	JUSTIFICATION FOR ENDPOINTS	PUTATIVE MECHANISMS OF ACTION
Primary			
To test the effects of a telephone-based peer mentor intervention on hospital resource utilizations	Composite count of ED visit and hospitalizations at the conclusion of the 12 to 18-month (T2) observation period comparing mentee group to usual care group.	Some visits made by patients on hemodialysis to the ED and subsequent hospitalizations may be avoidable with better outpatient care coordination and patient engagement. Peers may be best suited to provide support for patient activation.	Improvements in patient knowledge, self-efficacy, and skills related to self-care and connecting with their dialysis care team.
Secondary			
1) To test the effects of a mentor peer training program on the uptake of: a) dialysis knowledge and b) mentorship skills.	a) Change in scores on knowledge assessments after training (BL, 9M, 12-18M)  b) Uptake of skills involving	a) Knowledge in mentors is important to then disseminate to mentees through the peer intervention. These skills are in the causal pathway related to adherence behaviors.	Coaching skills by mentors to improve mentee knowledge, self-efficacy, communication skills and perceived social

OBJECTIVES	ENDPOINTS	JUSTIFICATION FOR ENDPOINTS	PUTATIVE MECHANISMS OF ACTION
	motivational interviewing, emotional support, non-judgmental listening and self-efficacy promotion in role playing exercises	b) An established method of training program evaluation includes assessments by the trainer during role playing of mastery of skills by the trainee.	support are hypothesized to increase activation to success in dialysis self-care.
2) To test the effects of a telephone-based peer mentor intervention on adherence behaviors, perception of self-efficacy, perception of social support and overall nutrition as possible mediators in the association of this intervention with primary outcomes	Month 3 & M-12 to 18 (T2) Intervention compared to UC a) Mean weekly missed minutes of dialysis; b) Mean monthly IDWG; c) Serum Alb; d) Self-efficacy; e) Social support; f) Knowledge	The effects of the peer intervention on adherence behaviors and perception of social support may alter the causal pathway(s) of high hospitalization rates in hemodialysis. Studies have shown an association between lack of patients' engagement and social support and adherence behaviors in patients on hemodialysis. Further studies have established the strong association between adherence behaviors and incidence of hospitalizations in this population.	Low perception of social support and low self-efficacy are associated with adherence behaviors and hospitalization outcomes.
Tertiary/Exploratory			
To test the feasibility and fidelity of a peer training program on mentor uptake	a. Attendance records of training sessions; b. Formative assessments of each training session	To inform future dissemination by characterizing the structural elements of the training program methods	n/a
To test the feasibility of the telephone-based intervention on mentees assigned to the intervention group	a) number and duration of telephone contact made by mentor/mentee; b) self-recorded content of mentor/mentee conversations;	Telephone records serve as the primary data to determine total dosing of intervention (minutes), as well as pattern of contact over the 3-month period	n/a

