### 1.3 SCHEDULE OF ACTIVITIES

Table 1. Mentor and Patient participant study activities

Mentors		Pre-screening (Pre-consent)	Visit 1 – Day 1	Training 1-4; Within 6-8 Weeks after V#1	Each Month	~Month 3, Month 10, as needed	Visit 2-Month 9 ± 30d	Visit 3-Mon 18 ± 30d; between 12-18M or at 12M depending on date	Final visit Month 18 ± 30d between 12-18M or at 12M depending on date
Review Eligibility		x							
Informed Consent			x						
Demographics			x						
Clinical history			x						
Baseline assessments			x						
Mentors (continued)									
Post training assessments (knowledge/formative/summative)			x						
Coordinator survey/check-in				x					
EMR Data Abstraction & Review				x					
Peer Mentor Refresher course (as needed)					x				
Optional social mixer or other group activity					x				
9-month follow-up assessments						x			
18-months follow up assessments							x		
Program evaluation interviews & field notes								x	

Time of the start of the intervention activity with the first mentee will determine the start of when subsequent study visits (9-month; 18-month, or between 12-18-months) will occur for mentors.

Intervention or Control Participants		Pre-screening	Visit 1	Each Month	Every 3-4 Months, as needed	Visit 2 Month 3 ± 30d	Visit 3 Month 18 ± 30d between 12-18M or at 12M depending on date	Final visit Month 18 ± 30d between 12-18M or at 12M depending on date
Review Eligibility		x						
Informed Consent			x					
Demographics			x					
Clinical history			x					

Baseline assessment surveys	x				
Kidney Disease Educational Materials	x				
Coordinator survey/check-in		x			
EMR Data Abstraction & Review		x			
3-month follow-up assessments				x	
18-month follow-up assessments, or between 12-18-months as noted depending upon enrollment date					x
Optional social mixer or group activity (intervention)			x		
Program evaluation interviews & field notes					x

Usual care group start time will begin at the time they receive the study kidney disease educational materials. Mentee group start time will begin at the time they receive their study phone and they are activated with their mentor.

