Refresher courses will be offered periodically, at approximately 3 months and 10 months after initial training or as needed for individual mentor's re-training. This will be at the discretion of the study team depending upon the information gathered during monthly and quarterly coordinator assessments of mentors (or mentee feedback). These refresher sessions will be approximately 2 hours, and be delivered in person, individually or in a group, or by video/webinar.

Trained mentors will receive a manual with all of the materials provided during training and this will serve as a reference for them throughout the study. There will be explicit support from the research team. It is possible that not all trained mentors will serve as intervention mentors and some may be assigned as 'back-up' mentors in the event an intervention mentor is not able to fulfil their role. Mentor selection will be discussed during training. The priority is optimizing the matching criteria between mentor/mentee pairs (sex, race (Hispanic, Black, White), age group ( $\pm 15$  years), and language). Selection criteria is not based on mentor performance during training. If matching criteria are not applied, then random selection of mentor assignments will be employed.

Assessments during the training will provide information both about feasibility and efficacy of the training on the desired knowledge, attitude and skill outcomes among mentors (See Section 8).

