#### Mentor Training Assessments

Mentors will be evaluated by *post-training* assessments. This will include the following:

- Fluid Training Survey (Module 1; 6 items)
- Uremia & Infection Training Survey (Module 2; 6 items)
- Mentor Role Training Survey (Module 3; 5 items)  
*Each of these survey items has one correct answer. Score will be reported as % correct overall.*
- Mentor Role Play Self-Assessment (Modules 3 & 4; 'Confident' Likert-type responses; 11 items)
- Formative Assessment after each module (Strongly agree to Strongly disagree; 11 items)
- Summative Assessment at the conclusion of core training (open ended questions; 5 items)

Refresher training events will only include formative and/or summative post-training assessments.

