**Table 4. Scientific Questions to be Addressed with the Trial**

Scientific question	Outcome(s)	Analysis
1. Does phone peer support improve outcomes at 18-months (*12 to 18-months)?	
 
Primary: composite endpoint count of ED visit and hospitalization events
 
Secondary: Various as listed above
 
	Poisson regression with two random intercepts. Random intercepts account for clusters by (1) mentor; (2) dialysis unit  See Section 9.4.2 (Primary); 9.4.3 (Secondary)
2. Is a peer mentor training program feasible?	
 
Attendance records
 
Pre- and Post-knowledge test scores
 
Satisfaction with training
 
Summative assessment
 
	Paired t-tests  Descriptive summaries and content analysis of qualitative data
3. Is a peer mentor training program accepted by patient receiving hemodialysis	
 
Satisfaction with intervention
 
Communication rating of mentors
 
	Descriptive  Content analysis of qualitative data

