#### Communication with providers

This is measured with the Communication Assessment Tool (CAT). There are 14 items with a response ranging from 1 to 5. The total score is the average of the 14 items. Question 15 is descriptive and not included in the overall score of the CAT.

*Feasibility Outcomes:* We will perform Wilcoxon rank sum test to test the difference in pre-and post-training knowledge assessments in the mentors (Baseline CHeKS; PLUS vs. 9M and 12 to 18M). The outcome variable for the regression is the difference between pre-and post-training scores and the parameter of interest is the intercept. We will test if the intercept is zero.

For qualitative data, we will review the content of the individual surveys and develop a novel coding scheme to characterize the content including common themes identified. We will also provide descriptive results of the HCCQ survey characterizing mentees' ratings of mentor communication.

---

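### The mentor knowledge endpoint captures what is retained after training, refreshers and mentoring together, so it cannot isolate the uptake produced by training

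*Combined protocol and SAP*

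**What the plan says.** - **Objective.** Table 3 (Section 3), secondary objective 1: "To test the effects of a mentor peer training program on the uptake of" dialysis knowledge (part a) and mentorship skills (part b). The endpoint for part a is "Change in scores on knowledge assessments after training (BL, 9M, 12-18M"). The synopsis (Section 1.1) also lists a pre/post knowledge change among the endpoints for feasibility of mentor training.
- **Contrast.** The feasibility paragraph of Section 9.4.3 sets pre- and post-training as "Baseline CHeKS; PLUS vs. 9M and 12 to 18M".
- **When the instruments are given.** Section 8.1 lists CHeKS and CHeKS PLUS for mentors at baseline (before training), 9 months and 12-18 months (T2).
- **Clock.** Section 1.3: "Time of the start of the intervention activity with the first mentee will determine the start of when subsequent study visits" occur for mentors. The 9-month visit has a window of 30 days either side.
- **Tests at training.** Section 8.1 lists three scored knowledge surveys under post-training assessments: "Fluid Training Survey (Module 1; 6 items"), a 6-item uremia and infection survey and a 5-item mentor role survey.
- **Refreshers.** Section 6.1.1 places them at about 3 and 10 months after initial training, or as needed. The synopsis and Section 6.1.2 count them as part of mentor training.
- **Back-up mentors.** Section 6.1.1: "It is possible that not all trained mentors will serve as intervention mentors".

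**The concern.** An effect of training on uptake needs a measurement before training and another soon after it, on the same instrument. The plan has no such pair. The instrument given before training is not repeated until well into the mentoring phase, and the instruments given at training have no listed pre-test.

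A gain at 9 months could come from the training, from explaining dialysis to mentees for months, from the mentor's own continuing treatment, or from weaker mentors having left. A flat result could mean that training failed or that knowledge was gained and then faded. The protocol presents the training as a reproducible program for wider use (Sections 2.3.2 and 3). A reader would naturally take a reported pre/post change as evidence that the curriculum works.

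**Working it through.** The plan gives no effect size, standard deviation or power for this contrast, so there is no figure of its own to reproduce. The check is one of timing.

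**Inputs**
- Core training: within 6-8 weeks after Visit 1 (Section 1.3).
- First repeat of CHeKS: first-mentee start + 9 months, ± 30 days, taken as ± 1 month (Section 1.3).
- T2: 12 to 18 months ± 30 days on the same clock.
- Refreshers: about 3 and 10 months after training (Section 6.1.1).
- Wait *g* from end of training to first mentee: not given. Assumed range 0 to 6 months.

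**Formulas, in months after the end of training**
- First repeat: from *g* + 9 − 1 = *g* + 8 to *g* + 9 + 1 = *g* + 10.
- T2: from *g* + 12 − 1 = *g* + 11 to *g* + 18 + 1 = *g* + 19.
- Time from the 3-month refresher to the first repeat: from *g* + 5 to *g* + 7.

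| Assumed *g* | First repeat | Time since 3-month refresher | T2 |
|---|---|---|---|
| 0 | 8-10 | 5-7 | 11-19 |
| 1 | 9-11 | 6-8 | 12-20 |
| 3 | 11-13 | 8-10 | 14-22 |
| 6 | 14-16 | 11-13 | 17-25 |

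The 10-month refresher precedes the whole 9-month window once *g* + 8 ≥ 10, that is, when *g* is 2 months or more. With a shorter wait it can fall on either side of that visit. T2 follows both scheduled refreshers even at *g* = 0, since 11 > 10.

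**Which instrument brackets the training?**

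| Instrument | Before training | Directly after training | Later |
|---|---|---|---|
| CHeKS, CHeKS PLUS | yes | no | 9 months, T2 |
| Module surveys (6 + 6 + 5 = 17 items) | not listed | yes | no |

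Neither row has both of the first two cells filled. Refresher sessions carry only formative or summative assessments (Section 8.1), so they add no knowledge score either. No group of untrained mentors is planned.

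**Mentors without a mentee.** The clock in Section 1.3 starts with the first mentee, and no start is given for a mentor who never has one. Each such mentor would be 1/20 = 5% of the synopsis number, or 1/17 = 5.9% of the number in Section 5. The documents do not say how many there will be.

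**The case against.** **Retained knowledge is a defensible target.** Table 3 justifies the endpoint by the mentor's need to pass knowledge on, so what a mentor knows during service matters. This stands as a reason to keep the 9-month and T2 scores. It does not make them a measure of uptake from training, which is what objective 1a names.

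**Refreshers and the manual belong to the program.** A reader might infer that refreshers contaminate the result. The synopsis and Section 6.1.2 count refreshers as training, and the manual is training material. Refreshers therefore block attribution to the four core sessions only. The stronger grounds are mentoring activity, continuing dialysis experience, possible attrition and the lack of a comparator.

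**Knowledge is tested at training.** Section 6.2.1 relies on knowledge surveys to confirm initial training, and Section 2.3.1 speaks of measuring knowledge at baseline and after training. The module scores do show attained knowledge. High module scores followed by a flat 9-month CHeKS would partly separate forgetting from failed training, so it goes too far to say that a null result is uninterpretable. But the instruments differ and no module pre-test is listed, so no change score results. The training manuals and manual of procedures were not available and might hold more.

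**Feasibility does not hang on this contrast.** A reader might infer that the feasibility conclusion fails with it. The documents do not support that: feasibility also uses attendance and course evaluations (Sections 1.1 and 3, Table 4), and Section 9.1 sets no hypothesis for it.

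**Loss of back-up mentors is an inference.** Section 1.3 is silent on their visits; it does not exclude them. About 100 mentees over 17 mentors is 100/17 ≈ 6 each over the study, so widespread non-activation looks unlikely. What remains is a clarification.

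**A test at the end of training would still be uncontrolled** and open to practice effects. This is true, but far fewer explanations compete over weeks than over 8 months or more.

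**Conclusion.** The point holds for the knowledge endpoint of secondary objective 1a. The only planned change score spans training, refreshers and mentoring together. Its first repeat comes at least about 8 months after core training, and 11 to 13 months after it if the first mentee arrives 3 months after training ends. That score describes knowledge retained over the whole period and cannot isolate the uptake produced by training.

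Two readings should be avoided. The interval is not 9 months of mentoring: it runs from the first mentee, each mentee period lasts 3 months, and actual mentoring may be less. Nor is 9 months the minimum, because the visit window allows 8.

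The conclusion assumes that mentoring starts only after training is complete (as Section 5 describes), that the window of 30 days is about one month, and that no module pre-test exists outside the documents. The improvement is worth making because it is cheap. Neither the primary endpoint nor the overall feasibility assessment depends on it.

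**What to change.** 1. **Mentors still to be trained.** Give CHeKS and CHeKS PLUS at the end of core session 4, with the post-training forms already collected there. Make baseline versus end of training the contrast for objective 1a in Table 3 and Section 9.4.3. Section 5.5 allows for new mentors during the study.
2. **The 9-month and T2 scores.** Keep them and label them retention.
3. **Mentors already trained.** Report their 9-month and T2 change as change over training, refreshers and mentoring, not as a training effect.
4. **Clarification in Section 1.3.** State when the 9-month and T2 visits fall for trained mentors who never receive a mentee.

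While this text is open, the test needs reconciling, which is a separate matter. Section 9.4.3 says "We will perform Wilcoxon rank sum test to test the difference in pre-and post-training knowledge assessments in the mentors", whereas Table 4 says "Paired t-tests". The scores are paired within mentor, and a rank-sum test is for independent samples.

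**Cost.** One more administration of two existing surveys for each mentor still to be trained, plus changes to the schedule and analysis wording. The short retest interval may add a practice effect, and nothing can be recovered for mentors already trained.

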## 4 STUDY DESIGN

### 4.1 OVERALL DESIGN

The goal of this study is to test the effects of a peer mentorship program on hospital utilization among high risk patients on hemodialysis as compared to a usual care control group. This is a two-arm pragmatic, randomized at the patient-level controlled trial. Exploratory analyses within the intervention arm will also be performed. Patients will be randomized in a 1:1 allocation and blinded to the research team until the disclosure of the randomization assignment. There will be enrollments in groups until each mentor has been randomly allocated their maximal number of mentees. Randomization will be computer generated and assigned by the coordinating center research team.

This is a multi-site trial, including dialysis units in Bronx, NY and Nashville, TN areas. The collaborating organizations include Albert Einstein College of Medicine (Coordinating Center) and Vanderbilt University Medical Center.

Intervention: Hemodialysis peer mentoring training and telephone coaching program.

The control group will receive kidney disease education about dialysis treatment adherence and access care in alignment with standard of care. Usual care will be at the discretion of the participant's clinical care team.

No interim analyses are planned.

### 4.2 RATIONALE FOR STUDY DESIGN

*Patient-level randomization.* We decided against cluster randomization because the threat of contamination of the intervention in this study with usual care is low. Additionally, dialysis facility location and culture is a potential confounding variable since the receptivity of the staff to patient requests and provision of care in response to patient self-management enhancement may be different between units. We also decided against this method because of feasibility and power considerations.

*Single blinded randomization.* Limitations to single blinding include patients speaking to staff and among themselves about their involvement with the study will be accounted for in the final analysis by tracking and adjusting for this variable through patient report. Using sequential multiple assignment randomization would enable better understanding of the different elements of the treatment on outcomes as this design assigns one element of an intervention only to those patients that have not responded to first in a series of interventions. We decided against using this method of randomization because of feasibility and the lack of rigorous evidence available to inform sequential program delivery.

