**Endpoints:**

Primary Endpoint: Composite count of ED visits and hospitalizations during 3 months of intervention and 15 months of follow up (18 months observation).

Due to the covid pandemic and recommendations from the DSMB, after 4/30 all participants' post-activity period follow up will be limited to 9 months (12 months of observation), or truncated to the current observation period total of between 12 and 18 months.

Secondary Endpoints:

- 1) Dialysis treatment adherence – mean missed minutes per month
- 2) Mean monthly inter-dialytic weight gain (%), serum albumin (g/dL);
- 3) Perceived self-efficacy, knowledge, perception of social support and quality of life.

Feasibility Endpoints (intervention only):

- 1) number of telephone contacts per week;
- 2) content of telephone conversations;

Feasibility of Peer Mentor Training:

- 1) attendance records for all sessions
- 2) change in pre-/post-knowledge assessments after training
- 3) content & descriptive evaluation of course evaluations

Peer mentorship to improve outcomes in patients on maintenance hemodialysis (PEER-HD) Version 3.0  
Protocol 2018-01  
30 April 2021

**Study Population:** 20 Mentor adult in-center hemodialysis patient participants  
200 Adult in-center hemodialysis patient participants  
Enrolled from dialysis units in or near the Bronx, NY and Nashville, TN

**Trial Type:** Pragmatic Randomized Trial

**Description of Sites/Facilities Enrolling Participants:** Participants are enrolled from multiple dialysis units affiliated with Albert Einstein (AECOM) College of Medicine and Vanderbilt University Medical Center (VUMC). AECOM will serve as the coordinating center.

**Description of Study Intervention:** Intervention will have 2 phases:  
1) **Mentor training**

- 4 Training sessions, 2 hours each covering topics in dialysis care, coaching and motivational interviewing techniques.
- Refresher 2-hour session at 3-months and 10-months
- Financial compensation by hour for training
- Assessments of skills, role modeling & simulations, exit interviews

2) **Telephone based 3-month intervention** by mentors for mentees

- Weekly phone contact with mentee (1-3 mentees per mentor)
- Social mixers at the dialysis facility, or other group activities

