## 6.3 MEASURES TO MINIMIZE BIAS: RANDOMIZATION AND BLINDING

We will randomize enrolled patient participants after completion of informed consent and the baseline visit utilizing a random number generator. As each subject is enrolled we will select envelopes with the random assignment to either the intervention or the usual care control group (1:1). The randomization will occur in blocks of between 28 to 42 depending upon the number of mentor and planned assigned mentees at the site. The goal is to have approximately equal total number of enrolled participants within each ~3-month intervention period. There may be staggering of the window and timeline depending upon enrollment pacing.

The mentee assignments will be blinded to usual care nephrologist and dialysis staff, but not to study subjects and mentors, because of the nature of intervention. The research team additionally will not be blinded to group assignment. While this may be preferred, it is not feasible in this pragmatic trial.

Enrolled participants will be encouraged to complete visit surveys on their own, to limit interactions with study staff in the process of data collection.

Trial randomization codes will be stored in a single file maintained by the data coordinating center. They will be shared with the research team as described above for patient participant assignment. Should accidental unblinding occur prior to completion of a baseline visit for a participant, the PI will be notified and this will be documented as a protocol deviation.

No change in study activities will occur in the event that it is identified that a usual care provider is unblinded to study assignment of their patient.

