#### 9.4.2 ANALYSIS OF THE PRIMARY ENDPOINT(S)

##### ED Visit and Hospitalization Count

Each month all enrolled patients will be evaluated for ED visit or hospitalization encounters by both self-report and medical record review. The events will be tabulated each month up to an 18-month period of follow-up. The rates of the composite event will be determined as event per patient-month and compared between the intervention and usual care group using Poisson regression with two random intercepts. In the regression model, the composite counts of ED visits and hospitalization during up to 18-months follow-up is the outcome variable and the intervention assignment of the mentees is the primary binary predictor. The log of follow-up time will be included as offset. The random intercepts will account for the correlation between mentees who share a common mentor as well as the correlation between mentees who are from a common dialysis facility (out of seven facilities). As a randomized controlled trial, we do not anticipate the need for covariate adjustment. However, if evaluation of patient characteristics by group identifies a failure of randomization and imbalance in key characteristics as an example including age, gender, comorbidity, race, or dialysis vintage they will be considered as adjustment variables in the analysis. We will control for type 1 error at 0.05. An exploratory analysis will consider the comparison between the groups but at 3-months of observation after the conclusion of the intervention delivery.

We will perform residual analysis for the mixed effects models. For mixed effects models, we will examine marginal residuals to check linearity and within-subjects covariance matrix and conditional residuals to check outliers as well as normality and homoscedasticity of the residual errors. In case Pearson residual analyses indicate overdispersion in the Poisson mixed effects model, we will perform quasi-Poisson model. We will use robust sandwich estimator in the presence of misspecification of the covariance matrix (i.e. random effects structure).

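### Section 4.2 promises to adjust the final analysis for patients' talk about the study, a post-randomisation variable that the primary model in 9.4 does not contain

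*Combined protocol and SAP*

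**What the plan says.** Section 4.2, in the paragraph on single-blinded randomisation, names as a limitation "patients speaking to staff and among themselves about their involvement with the study". It then says that this "will be accounted for in the final analysis by tracking and adjusting for this variable through patient report". It does not say which final analysis is meant, or how the variable is defined.

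The analysis sections read differently:

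- **9.3:** the primary comparison is by intention to treat.
- **9.4.1:** every analysis is adjusted for site, and other adjustment variables are to be pre-specified in the sections that follow.
- **9.4.2:** the primary model is a Poisson regression in which "the intervention assignment of the mentees is the primary binary predictor", with log follow-up time as offset and random intercepts for mentor and facility. On covariates it says: "As a randomized controlled trial, we do not anticipate the need for covariate adjustment". The exception is a failure of randomisation with "imbalance in key characteristics as an example including age, gender, comorbidity, race, or dialysis vintage they will be considered as adjustment variables".
- **6.4:** another post-randomisation variable, the dose of intervention received, is placed in secondary analyses.

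Section 6.3 says that "The mentee assignments will be blinded to usual care nephrologist and dialysis staff", but that participants, mentors and the research team know the assignment.

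**The concern.** Talk about the study cannot be a baseline characteristic. Patients in both arms know their assignment, and mentees have weekly calls and optional gatherings that usual-care patients do not have, so the amount of talk may well differ by arm. If talk also affects ED visits and hospitalizations, or shares causes with them such as severity or engagement, then conditioning on it replaces the randomised contrast with a different quantity. It does not recover an effect free of contamination.

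The second problem is ambiguity. Section 4.2 commits to an adjustment that 9.4 omits. An unblinded team could therefore defend either of two estimates from the same protocol after seeing results. What is at stake is the trial's main answer, the intention-to-treat rate ratio.

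**Working it through.** **1. The plan's own target.** Section 9.2 gives a control rate of 0.27 events per person-month, a 20% reduction (to 0.216) and 73 patients per group; 9.4.1 gives two-sided tests at 0.05. Section 9.2 does not state the follow-up, so 18 months, the full observation period, is assumed.

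- Person-months per group: 73 × 18 = 1,314. Expected events: 1,314 × 0.27 = 354.8 and 1,314 × 0.216 = 283.8.
- SE of the log rate ratio: √(1/354.8 + 1/283.8) = 0.0796.
- Power: Φ(0.2231/0.0796 − 1.96) = Φ(0.842) = 0.80.

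This reproduces the stated figure. The rate ratio of 0.80 is used below as the true effect. The figure does not depend on the adjustment, so removing the adjustment leaves it unchanged.

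**2. The sections side by side.**

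| Question | 4.2 | Elsewhere |
|---|---|---|
| Adjust for talk about the study? | Yes, in the final analysis | Not named in 9.4.1 or 9.4.2 |
| What may be adjusted for in the primary model? | – | Site (9.4.1); patient characteristics if randomisation failed (9.4.2) |
| How is it measured? | Patient report | No item among the assessments in Section 8 |

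The characteristics in 9.4.2 are given as examples, but the trigger is a failure of randomisation. A variable that arises afterwards does not fit that trigger.

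**3. What adjustment would do.** Let p_c and p_m be the proportions who talk in usual care and among mentees, and r the event rate ratio for talking within arm. The total rate ratio is the adjusted one times (p_m·r + 1 − p_m)/(p_c·r + 1 − p_c). Hence

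adjusted RR = 0.80 ÷ [(p_m·r + 1 − p_m)/(p_c·r + 1 − p_c)].

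None of p_c, p_m or r is in the documents; all are assumed. For p_c = 0.2 and p_m = 0.6:

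- r = 0.7: 0.80 ÷ (0.82/0.94) = 0.917
- r = 0.8: 0.80 ÷ (0.88/0.96) = 0.873
- r = 1.25: 0.80 ÷ (1.15/1.05) = 0.730

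On the log scale, the first two lose about 61% and 39% of the effect (ln 0.917 = −0.087 and ln 0.873 = −0.136, against ln 0.80 = −0.223). The third overstates it by about 41% (ln 0.730 = −0.315).

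| p_c, p_m | r = 0.7 | r = 0.8 | r = 1 | r = 1.25 |
|---|---|---|---|---|
| 0.2, 0.6 | 0.917 | 0.873 | 0.80 | 0.730 |
| 0.1, 0.7 | 0.982 | 0.912 | 0.80 | 0.698 |
| 0.2, 0.4 | 0.855 | 0.835 | 0.80 | 0.764 |
| equal | 0.80 | 0.80 | 0.80 | 0.80 |

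**4. Cross-check by simulation.** Poisson counts for 400,000 patients, again with assumed inputs: about 30% of controls talk, assignment multiplies the odds of talking by 4, and unmeasured severity has a log-rate SD of 0.5.

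| Scenario | Unadjusted RR | Adjusted RR |
|---|---|---|
| Talking has no effect; sicker patients talk more | 0.80 | 0.73 |
| Talking has no effect; sicker patients talk less | 0.80 | 0.88 |
| No treatment effect; sicker patients talk more | 1.00 | 0.91 |
| No treatment effect; sicker patients talk less | 1.00 | 1.10 |
| Talking lowers events (RR 0.8); no shared cause | 0.83 | 0.90 |
| Assignment does not affect talking; shared cause present | 0.80 | 0.80 |
| Assignment affects talking; no effect on events, no shared cause | 0.80 | 0.80 |

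The first four rows show that talk need not be a mediator for adjustment to mislead.

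**The case against.** The strongest reply is that 4.2 is a rationale section and speaks of the *final* analysis, not the *primary* one. The primary model is fixed in 9.3 to 9.4.2 and omits this variable, and 6.4 shows that the authors put another post-randomisation adjustment in secondary analyses. On this reading, the sentence simply never reached the analysis plan. That largely stands: a reader might infer from 4.2 that the primary comparison will be biased, and the documents do not support that. They support an unresolved conflict, because 4.2 carries no such restriction to secondary use.

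It can also be said that usual-care patients have study involvement to talk about: educational materials, monthly check-ins and paid visits. So a difference between arms is plausible, not established. That stands too, and it is why the no-bias cases belong in the table.

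Finally, an item on talking may exist in the manual of procedures or the check-in forms, which are not among the documents. The point about measurement is therefore limited to what Section 8 lists.

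**Conclusion.** The point holds as an inconsistency with a possible consequence. Section 4.2 promises an adjustment for an undefined post-randomisation variable that the primary model does not contain. If it entered that model, the intention-to-treat estimate could move either way: a true 0.80 would become about 0.73 to 0.92 with 20% and 60% talking and r from 0.7 to 1.25. The documents fix neither the size nor the direction, and under the two conditions shown above there is no bias.

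Two further inferences go beyond the text:

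- *Talk is on the intervention's own pathway.* Table 3 names as mechanism "Improvements in patient knowledge, self-efficacy, and skills related to self-care and connecting with their dialysis care team". Talk about study involvement may overlap with this, but 4.2 lists it as a limitation of blinding. It could equally be a marker of unblinding or contamination.
- *Gatherings on the unit reveal assignment to staff and so change ED use.* The synopsis does list "Social mixers at the dialysis facility, or other group activities", but 6.1.1 makes these optional and allows virtual ones. Section 6.3 already foresees unblinded usual-care providers, with no change in study activities. Nothing in the documents shows an effect on ED referral.

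**What to change.** In 4.2, keep the tracking and strike the adjustment. Alternatively, define the variable and its source, and limit it to a descriptive report by arm or a sensitivity analysis labelled as such. In 9.4.2, add that the primary intention-to-treat model includes no post-randomisation covariate, leaving site and baseline characteristics as the only candidates for adjustment.

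This changes wording only; the sample size and stated power are untouched. The cost is that any dilution from contamination stays uncorrected in the primary estimate and has to be discussed as a limitation. Section 4.2 itself rates the threat of contamination as low.
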